3.2 Data validation

Central data monitoring is performed by the IMF at the University of Fribourg. Data will be cleaned and validated by the data manager of the University of Bern. We will check for outliers, implausible values, and missing data, as well as inconsistencies. We will particularly check outcomes.

3.3 Data preparation

Outcomes will be created as explained in section 6.

3.4 Data sharing (if applicable)

Once the statistical analysis completed, data will be prepared for sharing and storage. Documents will include database and metadata (e.g., SAP, codebook, and statistical code). They will be sent back to the University of Fribourg. They will be shared on FAIR data repository, if requested by the sponsor-investigator.

4. Statistical Principles

4.1 Confidence intervals and *P* values

Statistical tests will be two-sided with a 5% significance level, except for the co-primary outcomes, for which a 2.5% significance level is used. We will present 95% confidence intervals, used to assess the precision of the estimates. We will not calculate p-values for baseline comparisons.

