2.3 Sample size

The sample size was calculated for each of the co-primary outcomes, using a Bonferroni correction for the significance level (.05 / 2 = .025). It was replicated in Stata 18 as follows:

- Reduction of symptom severity: Using a two-sample means test with power = 80%, a two-sided significance level = 2.5%, an allocation ratio 1:1, one day of difference between groups (Δ=1), and a standard deviation of 3 days assumed to be the same in both groups (1), we needed n=346 (173 in each group).
- Antibiotics use: Using a two-sample proportions test (Pearson's chi-squared test) with power = 80%, a two-sided significance level = 2.5%, an allocation ratio 1:1, a proportion of 60% in the control group and 45% in the intervention group (Δ =15) (2), we needed n=420 (210 in each group).

The largest sample size estimation was selected: n=420. As this approach is rather conservative (e.g., it does not consider the fact that the co-primary outcomes may be correlated), we did not account for potential drop-out in the sample size calculation.

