Handling of intercurrent events: All participants are included. Participants who took antibiotics at baseline will be considered as failures (having antibiotics).

Handling of missing data: Missing data will be multiple imputed (see section 6.4).

* Same adjustment as E1.1. If there are too few participants, we will use analyses adjusting separately for each covariate + type of recruitment.

Estimand E2.2: This estimand quantifies the efficacy of the treatment assessed with the proportion of antibiotics use (co-primary outcome) in the PP population.

Outcome of interest: same as estimand 2.1.

Population-level summary measure of outcome: same as estimand 2.1.

Participant-set of interest: PP.

Handling of intercurrent events: Participants with ICE1-3 are excluded from the analysis. The data will be weighted according to inverse probability weighting for ICE 1 and 2 (see section 6.2.2).

Handling of missing data: As ICE cannot be assessed in participants who drop out or are lost to follow-up, we will not use multiple imputation. We will use inverse probability of attrition weights to account for attrition and multiple imputation for missing baseline covariates (see section 6.4).

Estimand E3.1: This estimand quantifies the incidence of AEs and SAEs.

Outcome of interest: Presence of any adverse or severe adverse event (binary) during the follow-up (up to 22 days).

Population-level summary measure of outcome: adjusted^{*} hazard ratio.

Participant-set of interest: SAF.

Handling of intercurrent events: All participants are included.

Handling of missing data: No missing data, participants are censored when the study ends (at day 22) or at the day of last contact.

* 1) Adjusted for the type of recruitment (PCP/walk-in clinic) and 2) adjusted for the following factors at baseline: type of recruitment, age, sex, level of education, smoking status, beginning of symptoms (number of days), and baseline ABSS. If there are too few participants, we will use analyses adjusting separately for each covariate + type of recruitment.

Estimand E3.2: This estimand quantifies the incidence of AEs and SAEs.

Outcome of interest: same as estimand 3.1.

Population-level summary measure of outcome: same as estimand 3.1.

Participant-set of interest: SAF without ICE2.

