5.5 Withdrawal/follow-up

Withdrawal from the study and lost-to-follow-up will be summarized by percentage and n in each group.

6. Analysis

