6.2 Analysis methods

6.2.1 Primary analysis

The primary analysis will be done according to the FAS (ITT) and PP sets specified in section 4.2, using the adjusted model (4, 5). The randomization group will be used as the main predictor, adjusting for the stratification factors and relevant predefined covariates. To account for the fact that participants are clustered in PCP practices, we will use bootstrapped standard errors (1000 reps). A random seed will be predefined for replicability. The intraclass coefficient is expected to be small. All effects will be shown using marginal point estimates (accounting for adjustment variables) and 95% confidence intervals.

For the first co-primary endpoint, reduction in ABSS, we will use a linear regression, e.g.:

bootstrap, reps(1000) seed(XXX): regress y x1 x2

This endpoint should be normally distributed, as observed in previous studies (3). However, if it is not normally distributed, we will use a log-transformation after adding the constant 1.

For the second co-primary endpoint, *proportion of antibiotics use*, we will use a logistic regression, e.g.:

bootstrap, reps(1000) seed(xxx): glm y x1 x2, fam(bin) link(log) eform

We will use multiple imputation to handle missing values on covariates and outcomes (see section 6.4). If there is collinearity between covariates, we will remove one collinear variable based on theoretical reasons.

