6.4 Missing data

For missing data on outcomes and covariates, we use multiple imputation by chained equations (MICE), under the assumption of missing at random (MAR). Ten imputation datasets will be created

SAP for PHYTOBRONCH	Version of SAP: 1	
Based on template: CTU_STA_TEM-11; v5.0.0	Valid from: 20.03.2025	Page 14 of 15

and results pooled using Rubin's rule. The following auxiliary variables will be used to predict missingness: type of recruitment (PCP/walk-in clinic), age, sex, level of education, smoking status, beginning of symptoms (number of days), and baseline ABSS. Variables with missing values will be removed from the auxiliary list of variables. Terminal events such as death will be used as auxiliary variables. Technical issues (e.g., wrong email, reminder not sent) that cause missingness will also be used as auxiliary variables. For the PP analyses, we will also use inverse probability of attrition weights, which will be combined to inverse probability weights accounting for ICEs by a multiplication. We will use stabilized weights, truncated at the 99th percentile.

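### The co-primaries are tested at 2.5% but shown with 95% intervals, and the only example given for allowing no drop-out (correlated endpoints) adds no power to antibiotic use, which set N = 420

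*Combined protocol and SAP*

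**What the plan says.** **Test level and interval level.** Section 2.3 splits 5% by Bonferroni into 2.5% for each co-primary. Section 4.1 keeps that split for the tests, but its next sentence sets one interval level with no such exception. The general test level is 5%, with the co-primaries set apart, "for which a 2.5% significance level is used. We will present 95% confidence intervals, used to assess the precision of the estimates". Section 6.2.1, on the primary analysis, agrees: "All effects will be shown using marginal point estimates (accounting for adjustment variables) and 95% confidence intervals".

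**Drop-out.** Section 2.3 obtains 346 participants for ABSS and 420 for antibiotic use, and takes the larger. It then calls the approach rather "conservative (e.g., it does not consider the fact that the co-primary outcomes may be correlated), we did not account for potential drop-out". No other reason is named.

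The SAP does provide for incomplete outcomes. For antibiotic use in the full analysis set (section 4.3, estimand E2.1): "Missing data will be multiple imputed (see section 6.4"). Section 5.5: "Withdrawal from the study and lost-to-follow-up will be summarized by percentage and n in each group". Section 6.4 imputes outcomes and covariates in ten datasets, "and results pooled using Rubin's rule". No expected loss rate is given.

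**The concern.** **Display.** The Bonferroni split reaches the tests but not the intervals. Readers commonly judge a result by whether the interval contains no effect. For a co-primary with p between 0.025 and 0.05, that reading would contradict the SAP's own test, and both would appear in the same results table.

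**Power.** Section 2.3 offers conservatism in place of a drop-out allowance. That works only if the conservatism gives a reserve to the endpoint that needs one. Correlation between the endpoints affects the family-wise error. It does not affect the power of a single endpoint at a fixed level. If antibiotic use has no reserve, its 80% power holds only when every participant's outcome is known.

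**Working it through.** **Inputs (section 2.3).** Two-sided alpha 0.025 per endpoint, power 80%, 1:1 allocation. ABSS: difference 1 day, SD 3 days. Antibiotic use: 60% v 45%, Pearson chi-squared. Loss rates are assumptions.

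**1. The SAP's sample sizes reproduce.**
- Antibiotic use: n per arm = [z₁√(2p̄(1−p̄)) + z₂√(p₁(1−p₁)+p₂(1−p₂))]² / (p₁−p₂)², with z₁ = 2.241, z₂ = 0.842, p̄ = 0.525. This is [2.241√0.49875 + 0.842√0.4875]² / 0.0225 ≈ 209.4, so 210 per arm and 420 in total. Power is 80.1% at 210 per arm and 79.9% at 209.
- ABSS: the two-sample t-test (noncentral t) needs 173 per arm, 346 in total, with power 80.2%. At 210 per arm, power is 87.8%.

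**2. How often test and interval would disagree.** The chance of 0.025 < p < 0.05 is power at 0.05 minus power at 0.025, with 210 per arm, complete data and the planned effects.

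| Endpoint | Power at 0.05 | Power at 0.025 | Difference |
|---|---|---|---|
| Antibiotic use | 87.1% | 80.1% | 7.0% |
| ABSS | 92.6% | 87.8% | 4.8% |

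**3. Illustration (unadjusted).** Suppose antibiotics are used by 126/210 in control and 105/210 in intervention.
- Pearson chi-squared: p = 0.039, which fails at 2.5%.
- Risk ratio = 105/126 = 0.833. The standard error of its log is √(1/126 − 1/210 + 1/105 − 1/210) = 0.0891.
- 95% interval: exp(ln 0.833 ± 1.960 × 0.0891) = 0.700 to 0.992, which excludes 1.
- 97.5% interval: exp(ln 0.833 ± 2.241 × 0.0891) = 0.682 to 1.018, which includes 1.

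The width ratio on the log scale is 2.241/1.960 = 1.144. After pooling ten imputations with 5–20% missing information it is 1.144 to 1.145.

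**4. Power with loss of outcome information.** Power is recomputed at 210(1−d) per arm, with equal loss in both arms.

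| Assumed loss d | Antibiotic-use power |
|---|---|
| 0% | 80.1% |
| 2% | 79.2% |
| 5% | 77.9% |
| 10% | 75.4% |

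ABSS keeps at least 80% until 173 per arm remain: 1 − 173/210 = 17.6% loss.

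**5. What correlation does.** With both tests at 2.5% (bivariate normal), the family-wise error is 4.94% at correlation 0 and 4.65% at 0.5. The power of antibiotic use stays at 80.1% in both cases. Correlation would help only if the per-test alpha were reset to use it, which the SAP does not plan. Even then:
- At correlation 0.5, alpha becomes 0.0270, power is 80.9%, and 206 per arm would suffice.
- At correlation 0.9, alpha becomes 0.0350, power is 83.7%, and 192 per arm would suffice. With 10% loss, power is 79.4%.

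**6. Trial level.** The SAP does not say whether one positive co-primary is enough. If it were, power for at least one would be:

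| | Correlation 0 | Correlation 0.5 |
|---|---|---|
| Complete data | 97.6% | 94.0% |
| 10% loss | 96.0% | 91.4% |

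These figures are comfortable, but here correlation lowers power.

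**The case against.** **The intervals are for precision, not decision.** Section 4.1 says so, and no section uses an interval to decide. A single 95% level for all effects is a defensible reporting style. This stands, and it limits the point to display. It does not remove the point, because the results table would still pair a failed test with an interval that excludes no effect, and the SAP never says that conclusions rest on the 2.5% test alone.

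**Bonferroni is conservative, and correlation is only an example.** Both are true. Covariate adjustment, for instance, might add power. But section 2.3 neither names nor quantifies another source, and the example it gives does not help the endpoint that fixed N.

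**The power losses describe a simpler analysis.** They come from an unadjusted test with lost participants removed. The planned analysis adjusts for covariates and imputes outcomes, and antibiotic use is recorded both in the daily diary and at calls on days 4, 8 and 22 (section 6.1), so a missing diary need not mean a missing outcome. This also stands. The figures are approximate, their practical size cannot be settled from the SAP, and at 5% loss the shortfall is only about 2 points before any recovery.

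**The ABSS reserve is conditional.** It depends on the 3-day SD. Section 6.1 sets participants who never reach the 50% reduction to 22 days, and section 6.2.1 allows a log transformation, so that SD is not assured. Any power statement should carry its assumptions.

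**Conclusion.** Both parts hold. The interval level does not match the test level for the co-primaries. This is a reporting mismatch that does not inflate type I error, and a result with 0.025 < p < 0.05 remains non-significant under the stated rule. The 7.0% and 4.8% chances assume the planned effects and complete data.

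The drop-out reasoning does not support the choice it defends. The stated 80% power for antibiotic use is a complete-data figure with almost no margin, since one participant fewer per arm already takes it to 79.9%. How far it falls depends on a loss rate the SAP does not give and on how much imputation, adjustment and the phone calls recover. N = 420 is correct for its inputs, and ABSS has spare power under those inputs. The SAP should be corrected on both points, but neither changes the result of any test.

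**What to change.** **Section 4.1.** Replace the interval sentence with: *We will present 97.5% confidence intervals for the two co-primary outcomes, matching their 2.5% tests, and 95% intervals for all other effects.*

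**Section 6.2.1.** Use the same wording. Set the level in the final marginal estimate pooled by Rubin's rule as well as in the two bootstrap commands. If 95% intervals are also shown for the co-primaries, add: *Conclusions rest on the 2.5% test.*

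**Section 2.3.** Delete the correlation argument and write: *No drop-out allowance was made. Under the assumptions above and with 420 randomised, power for antibiotic use is 80.1% with complete outcomes, and about 78% at an assumed 5% and 75% at an assumed 10% loss of outcome information, before any recovery from imputation, covariate adjustment or the phone calls; ABSS keeps at least 80% up to about 17.6% loss.*

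**Cost.** Wording in three sections and an interval level in the code. Co-primary intervals become about 14% wider, and the stated power for antibiotic use is slightly less favourable. No change to N or to the testing procedure is needed.

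### Co-primary outcomes are tested at two-sided 2.5% but reported with 95% confidence intervals, so interval and test can disagree

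*Combined protocol and SAP*

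**What the plan says.** Section 2.3 sizes the trial for two co-primary outcomes, "using a Bonferroni correction for the significance level (.05 / 2 = .025"). Section 4.1 carries that split into the analysis. Its general rule is "Statistical tests will be two-sided with a 5% significance level", "except for the co-primary outcomes, for which a 2.5% significance level is used".

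For intervals, section 4.1 gives one level for everything: "We will present 95% confidence intervals, used to assess the precision of the estimates". Section 6.2.1, which sets out the primary analysis, has the same level: "All effects will be shown using marginal point estimates (accounting for adjustment variables) and 95% confidence intervals". It does not repeat the 2.5% level or mention p-values.

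No section provides a 97.5% or otherwise adjusted interval for the co-primary effects. None states that the 95% intervals are unadjusted for multiplicity, or that they do not correspond to the co-primary tests.

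**The concern.** A two-sided test at level α rejects exactly when the (1 − α) interval built from the same estimate, standard error and reference distribution excludes the null value. The interval that matches a 2.5% test is therefore the 97.5% interval. With 95% intervals there is a band of results, 0.025 < p < 0.05, in which the test says not significant and the printed interval excludes 0 days or a risk ratio of 1.

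At stake is how the two main results are read. Section 6.2.1 describes the display of effects only as point estimates with intervals, so a borderline result could be presented in two conflicting ways. If the plan does not settle the matter, someone may have to choose which of the two to stress after seeing the data.

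**Working it through.** **Inputs (section 2.3 unless noted).** Two-sided α = 0.025 per endpoint; power 80%; allocation 1:1. Symptoms: difference 1 day, SD 3 days. Antibiotics: 60% control, 45% intervention. N = 420, that is 210 per arm, with no allowance for drop-out. Interval level 95% (sections 4.1 and 6.2.1).

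**1. Reproduce the plan's sample sizes.**
- Symptoms: the normal formula n = 2·SD²·(z₀.₉₈₇₅ + z₀.₈₀)²/Δ² gives 2·9·(2.2414 + 0.8416)²/1² = 171.1, so 172 per arm. The noncentral t calculation gives 173 per arm, 346 in total, as stated.
- Antibiotics: with mean proportion 0.525, n = [2.2414·√(2·0.525·0.475) + 0.8416·√(0.60·0.40 + 0.45·0.55)]²/0.15² = 209.4, so 210 per arm, 420 in total, as stated.

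**2. Critical values.** z for two-sided 5% is 1.9600 and for two-sided 2.5% is 2.2414. The test and the 95% interval disagree when 1.9600 < |Z| < 2.2414. The ratio 2.2414/1.9600 = 1.144, so the matching interval is 14.4% wider.

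**3. Chance of disagreement at 210 per arm.** This is power at 5% minus power at 2.5%.

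| Endpoint | Power at 2.5% | Power at 5% | Difference |
|---|---|---|---|
| Antibiotics (chi-squared approximation) | 80.1% | 87.1% | 7.0% |
| Symptoms (noncentral t) | 87.8% | 92.6% | 4.8% |
| Symptoms (normal approximation) | 88.0% | 92.7% | 4.7% |
| Either endpoint under the null | 2.5% | 5.0% | 2.5% |

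**4. What it would look like (unadjusted illustrations, 210 per arm).**
- Symptoms: SE = 3·√(2/210) = 0.293 days. For a difference of −0.62 days, |Z| = 2.12 and p = 0.034. The 95% interval is −0.62 ± 0.574, or −1.19 to −0.05, which excludes 0. The 97.5% interval is −0.62 ± 0.656, or −1.28 to +0.04, which includes 0.
- Antibiotics: 104/210 against 126/210 gives RR = 0.825. The SE of log RR is √(1/104 − 1/210 + 1/126 − 1/210) = 0.0896, so |Z| = 2.14 and p = 0.032. The 95% interval is 0.692 to 0.984, which excludes 1. The 97.5% interval is 0.675 to 1.009, which includes 1.

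**5. Family-wise error, only if the intervals were used as tests.** With independent endpoints and no effect on either, the chance that at least one 95% interval excludes no effect is 1 − 0.95² = 9.75%. With 97.5% intervals it is 1 − 0.975² = 4.94%. Over other degrees of positive or negative dependence, the figure for 95% intervals runs from 5% (the two endpoints always agree) to at most 0.05 + 0.05 = 10%.

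**The case against.** The strongest reply is that the plan gives test and interval different jobs. Section 4.1 assigns significance to the tests and describes the intervals as a measure of precision. A 95% interval is a valid statement of precision for a single parameter, so on this reading nothing is contradicted. That is a fair account of section 4.1, and it limits the point to reporting. It does not remove it: a stated purpose of precision does not stop an interval from visibly excluding no effect, and the plan nowhere says that the co-primary intervals are unadjusted.

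A reader might go further and infer that the 95% intervals undo the multiplicity correction, or that the trial runs a 9.75% family-wise error. The documents do not support this. The correction acts through the 2.5% tests, which hold family-wise error to at most 5% whichever interval is printed, and neither power nor n = 420 depends on the interval level. The 9.75% applies only if the intervals are used as tests and the endpoints are independent, whereas section 2.3 itself notes that they may be correlated.

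Two technical objections also stand. The 7.0% and 4.8% are planning figures; the actual analysis is covariate-adjusted, with bootstrapped standard errors and multiple imputation. And because section 6.4 pools ten imputed datasets by Rubin's rules, a 97.5% interval cannot be had simply by multiplying one bootstrap standard error by 2.241 or by reading off raw bootstrap percentiles: either would ignore the between-imputation variance.

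**Conclusion.** The point holds as an inconsistency in reporting and interpretation. The interval level in sections 4.1 and 6.2.1 does not match the co-primary test level in section 4.1, and any co-primary result with p between 0.025 and 0.05 would be non-significant beside an interval that excludes no effect.

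Its size is modest: about one chance in 14 for antibiotics (7.0%) and one in 21 for symptoms (4.8%) if the design effects are true, and one in 40 (2.5%) per endpoint if there is no effect. These figures assume the planning rates and SD, 210 analysed per arm, no covariate adjustment and no missing data. Exact limits will differ in the real analysis, but the mismatch itself needs only that test and interval come from the same estimate, standard error and reference distribution.

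The tests and the sample size need no change. The correction is worth making because it concerns the two main results and costs almost nothing.

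**What to change.** In sections 4.1 and 6.2.1:

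- Report 97.5% confidence intervals for the co-primary effects, estimands E1.1 and E2.1. Compute them from the Rubin-pooled estimate and standard error (on the log scale for the risk ratio) with the matching 97.5% reference quantile: about 2.24, or the t quantile with Rubin's degrees of freedom.
- State that the conclusion on each co-primary outcome rests on p < 0.025.
- Label any 95% interval also shown for these two outcomes as unadjusted for multiplicity.
- Keep 95% intervals for the secondary outcomes.

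The cost is a short amendment to each of the two sections and intervals about 14% wider for the two co-primary effects; for symptoms at SD 3 days and 210 per arm, the half-width goes from 0.574 to 0.656 days. Sample size, models, tests and data collection are unchanged. The change should be made before the outcome data are analysed, so that the interval level is not chosen in the light of a borderline result.

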4.2 Analysis populations

4.2.1 Full analysis set (FAS)

The full analysis set (FAS) will include all randomized participants, regardless of protocol violations or discontinuation. Analyses will be conducted following the intention-to-treat (ITT) principle, with participants analyzed according to their assigned group.

For the secondary outcome on PCPs, the FAS will include all PCPs invited to participate in the trial, regardless their answer.

SAP for PHYTOBRONCH	Version of SAP: 1	
Based on template: CTU_STA_TEM-11; v5.0.0	Valid from: 20.03.2025	Page 7 of 15

